6.5. Concomitant Therapy

Any medication or vaccine (including over-the-counter or prescription medicines, vitamins, and/or herbal supplements) that the participant is receiving at the time of enrollment or receives during the study must be recorded along with:

- Reason for use
- Dates of administration including start and end dates.

Patients receiving selpercatinib should avoid concomitant use of CYP2C8-sensitive substrates. If co-administration of a CYP2C8-sensitive substrate cannot be avoided, monitor patients for increased adverse reactions of these drugs.

Caution should be used when co-administration of a P-gp substrate (for example, fexofenadine, loperamide, and digoxin), MATE1 substrate (for example, metformin), or BCRP substrate (for example, sulfasalazine) cannot be avoided in patients receiving selpercatinib. Consider increased monitoring as appropriate. The concurrent use of drugs known to prolong QTc is prohibited (Appendix 7). Drugs with a possible or conditional risk should be avoided if possible. Patients eligible to receive vandetanib should refrain from sun exposure during and up to 4 months after discontinuation of treatment due to possible photosensitivity.

The Lilly medical team should be contacted if there are any questions regarding concomitant or prior therapy. Except as indicated in Section 6.1, patients are not allowed to receive concomitant systemic anti-cancer agents (including immunotherapy agents), hematopoietic growth factors for prophylaxis in C1, drugs with immunosuppressant properties (other than as listed in Section 6.5.4), or any other investigational agents. No new, alternative systemic anticancer therapy is allowed prior to documentation of PD in accordance with protocol specified disease response criteria. No surgical resection of tumor or radiation therapy is permitted except as described in Section 6.5.4.

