7.1. Discontinuation of Study Intervention

Possible reasons leading to permanent discontinuation of investigational product:

- **Subject Decision**
 - the participant or the participant's designee, for example, parents or legal guardian requests to discontinue investigational product.

If a clinically significant finding is identified after enrollment, the investigator or qualified designee will determine if the participant can continue in the study and if any change in participant management is needed.

In addition, participants will be discontinued from the investigational product in the following circumstances:

- the patient becomes pregnant during the study. See Section 8.3 regarding regulatory reporting requirements on fetal outcome.
- the patient is significantly noncompliant with study procedures and/or treatment
- disease progression (radiographic or clinical progression). Patients with disease progression per investigator assessment may continue treatment while awaiting BICR confirmation of progression. Exceptions for continuing study treatment beyond suspected radiographic progression may be made on a case-by-case basis for patients who are believed to be clinically benefiting from study treatment, and the investigator and Lilly medical team agree that continuing study treatment is in the patient's best interest. Expectations for required study procedures and data collection for each patient will be made at the time of approval.
- the patient experiences unacceptable toxicity from study treatment
- the patient, for any reason, requires treatment with another therapeutic agent that has been demonstrated to be effective for treatment of the study indication. Discontinuation from study treatment will occur prior to introduction of the new agent
- the investigator decides that the patient should be discontinued from study treatment.

Participants discontinuing from the investigational product for any reason should complete AE and other follow-up procedures, including imaging assessments, per Section 1.3 (Schedule of Activities), Section 8.3 (Adverse Events and Serious Adverse Events), and Section 8.2 (Safety Assessments) of the protocol.

Participants assigned to treatment Arm B who experience progression may cross-over to selpercatinib after meeting criteria in Section 5.2.1 and comply with procedures noted in Section 1.3.

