For each modality, IV and oral contrast should be utilized (chest CT does not require contrast) unless there is a clear contraindication (e.g., decreased renal function or allergy that cannot be addressed with standard prophylactic treatments). Post-baseline imaging should be performed every 8 weeks (± 7 days) for 24 weeks and every 12 weeks (± 7 days) thereafter, including imaging of the neck, chest, abdomen, and pelvis, and any other known sites of disease, using the same modality(ies) as used for baseline imaging obtained during the screening period until PD, withdrawal of consent, or death. For the purpose of determining progression for eligibility, a change in modality *may* be acceptable if clear progression can be confirmed by central review, especially when a less sensitive modality was used for the second scan (e.g., liver metastases present on CT abdomen occurring after a previously normal MRI abdomen). Additional studies can also be performed at any time as clinically indicated. Please see the Site Imaging Manual for guidelines on how the various imaging studies should be performed and transmitted for central review.

For patients who progress on study treatment and begin a different anti-cancer therapy (including patients who are initially assigned to the control arm and crossover to receive seliperatinib), PFS2 will be collected. It is recommended to maintain the study imaging schedule in patients who have discontinued treatment; that is, to continue imaging every 8 weeks for the first 24 weeks of the next therapy, then every 12 weeks, as much as allowed according to the patient's new treatment standard of care. These images will be collected centrally and the overall tumor assessment should be entered into the CRF.

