9.4.3.3. Other Secondary Analyses

Overall response rate will be assessed for Arm A versus Arm B using a Cochran-Mantel-Haenszel test stratified by the randomization strata.

- ORR per RECIST 1.1 as assessed by BICR
- ORR per RECIST 1.1 per investigator assessment

The following secondary outcomes will be assessed for Arm A vs. Arm B using a logrank test stratified by the randomization strata. The corresponding HR between treatment arms will be estimated using a stratified Cox regression model (Cox 1972), stratified by the randomization strata. Point estimates with 95% CI, for each treatment arm will be estimated using the Kaplan-Meier method (Kaplan and Meier 1958):

- TFFS as assessed by investigator
- PFS as assessed by investigator
- DoR as assessed by investigator
- DoR as assessed by BICR
- PFS2 as assessed by investigator

Progression-free survival per investigator assessment is defined in the same manner as BICR PFS.

TFFS per investigator assessment is defined as the time from randomization to the first occurrence of documented radiographic disease progression per RECIST 1.1 as assessed by the investigator or unacceptable toxicity leading to treatment discontinuation as assessed by the investigator (regardless of a study drug-related AE meets protocol guidance for treatment discontinuation or not); or death (due to any cause).

Progression-free survival 2 (PFS2) is defined as the time from randomization to disease progression (radiographic or symptomatic progression as determined by the investigator) on the next line of treatment or death from any cause in the absence of observed disease progression. If the patient is alive at the cutoff for analysis, and disease progression has not been observed, PFS2 data will be censored on the latest date of last progression-free assessment or start of the next line of treatment.

Duration of response (DOR) is defined as the time from the date that measurement criteria for complete response (CR) or partial response (PR) (whichever is first recorded) are first met by the BICR or investigator assessment, as applicable, until the first date that disease is recurrent or documented disease progression is observed, per RECIST 1.1 criteria, or the date of death from any cause in the absence of documented disease progression or recurrence.

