Overall survival will be compared between treatment arms using a stratified logrank test, stratified by the randomization strata. The corresponding HR between treatment arms will be estimated using a stratified Cox regression model (Cox 1972), stratified by the randomization strata. Overall survival curves, the median and OS rates at various time points with 95% CI, for each treatment arm will be estimated using the Kaplan-Meier method (Kaplan and Meier 1958).

Multiple sensitivity analyses for the OS will be conducted as defined below:

- using an unstratified logrank test and an unstratified Cox regression model
- using stratification factors based on the eCRF data
- repeating the main OS analysis for the PP population
- censoring OS at start of new systemic anticancer therapy including crossover therapy for patients assigned to Arm B who crossed over to selpercatinib
- censoring OS for crossover patients at start of crossover therapy for patients assigned to Arm B who crossed over to selpercatinib
- censoring OS for patients who continued study therapy beyond progression at the earliest date of study therapy after tumor progression by BICR.

Progression-free Survival 2

Progression-free survival 2 is defined as the time from randomization to disease progression on the next line of treatment or death from any cause in the absence of observed disease progression. If the patient is alive at the cutoff date for the analysis, and disease progression has not been observed, PFS2 data will be censored on the latest date of last progression-free assessment or start of the next line of treatment. [Table JZJB.10](#) defines censoring rules to be applied to the PFS2 analysis.

Progression-free survival 2 will be compared between treatment arms using a stratified logrank test, stratified by the randomization strata. The corresponding HR between treatment arms will be estimated using a stratified Cox regression model (Cox 1972), stratified by the randomization strata. Progression-free survival 2 curves, the median and PFS2 rates at various time points with 95% CI, for each treatment arm will be estimated using the Kaplan-Meier method (Kaplan and Meier 1958).

Table JZJB.10. PFS2 Censoring Scheme

Situation	Event/Censor	Date of Event or Censor
Tumor progression ^a or death on the next line of treatment	Event	Earliest date of PD or death

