No tumor progression and no death on the next line of treatment	Censored	Latest date of last progression-free assessment or start of the next line of treatment
	Unless	
No baseline radiologic tumor assessment available	Censored	Date of randomization
Patient is still on study treatment	Censored	Date of last progression-free assessment
Patient discontinued the study treatment but has not started next line of treatment or		
Patient had tumor progression on study treatment but has not discontinued		
1. death	1. Event	1. Date of death
2. patient is alive	2. Censored	2. Last date the patient is known to be alive
No tumor progression prior to the start of the next line of treatment	Censored	Date of last progression-free assessment prior to the start of the next line of treatment

Abbreviations: PD = progressive disease; PFS = progression-free survival; PFS2 = progression-free survival 2; RECIST 1.1 = Response Evaluation Criteria in Solid Tumors, version 1.1.

^a Symptomatic deterioration (that is, symptomatic progression that is not radiologically confirmed per RECIST 1.1 criteria) will be considered as tumor progression.

- If there are multiple dates associated with 1 assessment, the assessment date will be set to the first date when the overall response is PD and the last date otherwise.

Adverse Events

The Medical Dictionary for Regulatory Activities (MedDRA) preferred term (PT) derived from the verbatim term will be used when reporting AEs by MedDRA terms. The MedDRA Lower Level Term (LLT) will be used in the treatment-emergent computation. Severity will be measured using the grade defined by the National Cancer Institute - Common Terminology Criteria for Adverse Events (NCI-CTCAE) version 5.0.

Treatment-emergent adverse events (TEAEs) are events that first occurred or worsened in severity after baseline and up to 30 days after core period treatment discontinuation.. Treatment-emergent adverse events will be summarized by System Organ Class (SOC) and by decreasing frequency of PT within SOC. TEAE after crossover will be defined and summarized separately in Section 8.5.

Serious adverse events (SAEs) are any AEs that result in any of the following outcomes:

- death
- initial or prolonged inpatient hospitalization
- a life-threatening experience (ie, immediate risk of dying)
- persistent or significant disability/incapacity
- congenital anomaly/birth defect
- important medical events (detailed description is contained in the protocol)

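### The last row of the PFS2 censoring table discards progression and death on the next line for patients who start it without prior progression, contrary to the PFS2 definition

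*SAP*

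**What the plan says.** **Definition.** SAP Section 8.4.2 states: "Progression-free survival 2 is defined as the time from randomization to disease progression on the next line of treatment or death from any cause". Protocol Section 9.4.3.3 has the same structure and specifies "radiographic or symptomatic progression as determined by the investigator". Neither text makes progression before the next line a condition.

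**Censoring sentence.** For living patients without observed progression, both documents use the later of two dates. In the protocol's words, "PFS2 data will be censored on the latest date of last progression-free assessment or start of the next line of treatment".

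**Table JZJB.10.** The first row makes progression or death on the next line an event. The second censors event-free patients by the later-of-two-dates rule. A block of exceptions follows under "Unless". The last exception covers patients with no tumor progression before the next line began and censors them at the "Date of last progression-free assessment prior to the start of the next line of treatment".

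**Data collection.** Protocol Section 8.1.1 describes PFS2 collection "For patients who progress on study treatment and begin a different anti-cancer therapy", a narrower group than the definition covers.

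**The concern.** PFS2 is meant to carry the randomized comparison through the next line of therapy. For patients who switch without progression, the last row ends observation before that line begins, so their next-line outcome cannot enter the analysis. Two things are at stake.

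- **Ambiguity.** Two analysts, one following the definition and one the table, would assign different event status and different dates to the same patient.
- **Informative censoring.** Patients who leave study treatment early for another agent may differ in prognosis from those who stay. Censoring them at the switch treats them as exchangeable with the rest.

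PFS and TFFS have sensitivity analyses that count events after new systemic therapy (SA2 in Table JZJB.4, SA5 in Table JZJB.8). PFS2 has none, so no planned analysis recovers the lost events.

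**Working it through.** The documents give no event count, power or effect size for PFS2, so there is no plan figure to reproduce. The main check is a comparison of texts.

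**1. One patient under each rule.** A patient stops study drug for toxicity without progression, starts another agent, and dies on it.

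| Source | Status | Date |
|---|---|---|
| Definition (SAP 8.4.2, Protocol 9.4.3.3) | Event | Death |
| Table JZJB.10, first row | Event | Death |
| Table JZJB.10, last row (overrides) | Censored | Last progression-free assessment before the next line |

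If the same patient is alive and progression-free on the new agent, the censoring sentence gives the next-line start or a later assessment. The last row gives an earlier date. The table also treats similar patients differently: one who stops without progression, starts nothing and dies is an event, but one who starts another drug and then dies is not.

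**2. Can the row apply?** Protocol Section 6.5 states "No new, alternative systemic anticancer therapy is allowed prior to documentation of PD". Section 7.1 allows stopping for unacceptable toxicity, or because another effective agent is needed, in which case "Discontinuation from study treatment will occur prior to introduction of the new agent". SAP Table JZJB.1 lists anticancer therapy after discontinuation and before a PFS event as an expected intercurrent event. The row is therefore not empty, but no frequency is given. Crossover should not trigger it, because Protocol Section 5.2.1 requires BICR-confirmed progression and allows no exception to that criterion.

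**3. Ceiling on the count.** Inputs are about 250 patients at 2:1, so 167 selpercatinib and 83 control (Protocol 4.1), and historical cessation of 12% on vandetanib and 16% on cabozantinib (Protocol 2.2). Assume every cessation leads to a next line without progression.

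- Control: 0.12 × 83 = 10.0; 0.16 × 83 = 13.3, or about 10-13 patients.
- Selpercatinib: Protocol 2.3 calls the rate low and gives no figure. At an assumed 2%, 4% and 8% of 167, the counts are 3.3, 6.7 and 13.4.
- Selpercatinib rate giving equal counts: 10.0/167 = 6.0% to 13.3/167 = 8.0%.

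**4. Illustrative simulation.** Assumptions: exponential PFS with medians of 50 and 25 months (Protocol 9.2), switch without progression at months 1-12, next-line median of 12, 24 or 48 months in both arms, and follow-up of 24-72 months. As a simplification, the row was applied at next-line start rather than at the preceding scan.

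| Assumed switch rate, selpercatinib / control | HR by definition | HR by table row | PFS2 events lost, selpercatinib / control |
|---|---|---|---|
| 2% / 12% and 4% / 16% | 0.46-0.56 | 0.50-0.58 | 4-10% / 15-22% |
| 8% / 16% | 0.52-0.57 | 0.50-0.55 | 18-19% / 19-22% |

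The row moves the HR toward 1 in the first line and away from 1 in the second. Repeat runs kept the sign in each scenario, but the reversal is small. Switching was simulated as unrelated to prognosis, so these figures do not measure informative censoring.

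**The case against.** The strongest defence is that the row is deliberate. Protocol Section 8.1.1 ties PFS2 collection to patients who have progressed. For a patient who has not, progression on the next line is the first progression rather than the second. The row also parallels the PFS and TFFS rules, which censor at new systemic therapy. This explains the row, but it does not remove the conflict. The restriction appears in neither definition, and it cannot justify ignoring a death when the definition counts death from any cause.

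A reader might infer more than the documents support:

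- **That all follow-up is lost.** Follow-up to the last assessment before the next line is kept; only what comes later is discarded.
- **That the control arm is mainly affected and the comparison is biased in a known direction.** Cessation is not the same as starting a next line before progression. Imaging continues after discontinuation, and a patient who progresses off treatment before switching does not meet the row. No selpercatinib rate is given, and the simulated shift changes sign with the assumed rates.
- **That the last-known-alive rows are also wrong.** They cover patients who have started no next line, or who progressed but remain on study drug. Until a next line starts, death is the only possible PFS2 event, so last-known-alive is a sensible date. Applying the definition's dates there could censor a progressed patient before the progression itself.

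**Conclusion.** The contradiction stands on the text alone, whatever the rates prove to be. The last row of Table JZJB.10 conflicts with the PFS2 definition in both documents, the censoring sentence and the table's first row, and Protocol Section 8.1.1 must be reconciled with them.

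The size is unknown. The 10-13 of 83 control patients are a ceiling that rests on every historical cessation leading to a next line before progression; they are not an estimate. Unequal impact between arms is plausible from the cessation rates but is not shown.

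The consequence is limited. PFS2 lies outside the tested sequence of PFS, TFFS and comparative tolerability (SAP 8.8), and these patients' deaths still count in OS. The change is worth making because it is specific and cheap, but it does not bear on the primary conclusion.

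**What to change.** 1. In the main PFS2 analysis, delete the last row of Table JZJB.10. The first two rows then apply: next-line progression or death from any cause is an event, and event-free patients on a next line are censored at the later of the last progression-free assessment or next-line start.
2. Keep the current row only as a named PFS2 sensitivity analysis.
3. Reword Protocol Section 8.1.1 so that PFS2 is collected for every patient who starts a next line.
4. Leave the last-known-alive rows unchanged.

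**Cost.** A SAP table edit, one extra sensitivity run and a wording change in the protocol. Deaths are already collected for OS. The downside is that, for these patients, progression on the next line is their first progression. Some of those dates may be incomplete, because Section 8.1.1 does not clearly require their collection and next-line imaging follows local standard of care. The report should state how many patients are affected in each arm.
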